A feasibility study addressing the adjunct use of Low-Level Laser to Mayo Lifestyle Modification Education and Wellness Coaching for Reducing Central Adiposity and Fat Mass

NCT05083442

22 Nov 2024

General Study Information

Principal Investigators: [name].

[figure not shown]
Co-Principal Investigators: [name]., M.D.

Study Title: A feasibility study addressing the adjunct use of Low-Level Laser to Mayo Lifestyle Modification Education and Wellness Coaching for Reducing Central Adiposity and Fat Mass

Protocol version number and date: Version 2, 22 Nov 2024

Research Question and Aims

Hypothesis: We hypothesize that the addition of Lifestyle Modifications as well as Wellness Coaching counseling during LLLT treatments targeting central adiposity body regions will produce a **greater fat mass loss** when compared to Lifestyle Modifications and Wellness Coaching alone:

Aims, purpose, or objectives: The overarching purpose of this study is to obtain preliminary evidence regarding the efficacy of LLLT treatments for obtaining fat mass loss and to produce a reduction in waist circumference by week 6 (end of treatment).

Primary Aim:

To compare the amount of fat mass loss at the end of week 6 (end of LLLT treatment) for people who are overweight and obese who are receiving Wellness Coaching with lifestyle modifications, with and without adjunct LLLT.

Secondary Aim:

[figure not shown]
To compare the change in waist circumference from baseline, at the end of week 6 (end of LLLT treatment) for people who are overweight and obese who are receiving Wellness Coaching and lifestyle modification instruction, with and without adjunct LLLT.

Background: Overweight and obesity are defined as abnormal or excessive fat accumulation that may impair health, leading to reduced life expectancy and/or increased health problems¹, and results from an energy imbalance. In basic terms, *obesity* is defined as having more body fat than is considered healthy², which, in turn, is defined as a body mass index (weight (kg)/height (m)²) of 30.0 or higher³. Currently in the United States, about 38% of the American adult population is considered obese³⁻⁷, which translates to one in three Americans being obese.

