Clinically, the LLLT treatments can vary from 6 to 28 treatments and a frequency of 1-3 times per week depending on the patients' preference and ability to pay. Our research team conducted a previous feasibility study of 45 overweight/obese subjects looking at the use of 12 LLLT treatments over the course of 12 weeks (one treatment per week) with the end goal of reducing central adiposity. In this prior study (IRB 14-002370), subjects were randomized to 1 of 3 conditions (LLLT, lorcaserin, and LLLT + lorcaserin). This study demonstrated feasibility by recruiting the goal of 45 obese subjects within 3 months. The subjects assigned to LLLT did not have any adverse events reported during the 6 months of the trial and although the sample size was too small for any significant findings, the LLLT did show a reduction in body circumference (2.3 to 4.0 cm reduction) and a reduction in weight (1 to 3.5 kg reduction). This 2014 study was followed by another study (IRB 16-004817) in which our study team compared different frequencies of administering 12 LLLT. The compared frequencies were 12 treatments administered once per week, twice per week or 3 times per week. This latter study found that 12 treatments delivered twice per week (for up to 6 weeks) was the most optimal⁸ frequency when considering maintenance of the weight loss post treatment. Although weight loss and inches lost were significant with LLLT, a theory does exist that when LLLT is accompanied by lifestyle modification, including a reduction in dietary intake as well as an increase in caloric expenditure through moderate-intensity activity, the impact of the weight and inches lost will be greater. The overarching goal of this study is to test this hypothesis.

For the purposes of this study, we will define overweight as having a body mass index [BMI] of 25-29.9 kg/m² and obesity as a BMI of 30-39.9 kg/m². In this pilot study we will randomize 60 overweight and obese individuals to one of two treatment arms:

- LLLT + Lifestyle Modifications and Wellness Coaching (GROUP 1),
- Sham LLLT + Lifestyle Modifications and Wellness Coaching (GROUP 2).

Study Design and Methods

Methods:

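### Does the Background set the trial a goal that its two arms cannot meet?

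*Combined protocol and SAP*

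**What the plan says.** The Background reviews the team's earlier laser studies and then reports that "a theory does exist that when LLLT is accompanied by lifestyle modification, including a reduction in dietary intake" and more physical activity, the loss of weight and inches will be larger. The next sentence reads "The overarching goal of this study is to test this hypothesis".

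The arms follow in the same section: "In this pilot study we will randomize 60 overweight and obese individuals to one of two treatment arms". Group 1 receives active laser and Group 2 sham laser. Both receive the lifestyle programme and coaching.

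The Hypothesis under Research Question and Aims begins "We hypothesize that the addition of Lifestyle Modifications as well as Wellness Coaching counseling during LLLT treatments targeting central adiposity body regions" and predicts greater fat mass loss "when compared to Lifestyle Modifications and Wellness Coaching alone".

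The Primary Aim compares week 6 fat mass loss, with or without laser, in people who all receive the programme. The Secondary Aim does the same for waist circumference. Study Design calls laser an adjunct to the programme. The Data Analysis Plan compares the two groups on change in fat mass by analysis of covariance, adjusting for baseline. The Sample-size Justification is for laser against sham.

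**The concern.** The theory in the Background concerns what lifestyle change adds to laser. Its sentence opens by noting that laser already gave significant losses in the earlier work, so greater can only mean greater than with laser unaccompanied. Testing that requires people on laser with the programme and people on laser without it. The randomized contrast runs the other way: laser varies and the programme is held constant. The Hypothesis seems to repeat the problem, because it too opens with "the addition of Lifestyle Modifications as well as Wellness Coaching counseling during LLLT treatments" as the thing that is added.

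If that really were the question the trial must answer, the design would be unable to answer it. A positive result could be read as showing that lifestyle change enhances laser, and a null result as refuting it, with neither reading supported by the data. Statistical Considerations says the results will help decide whether further studies are warranted and help design a larger trial, so the misreading could carry forward.

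**Working it through.** **What each arm identifies.** Write L for laser (1 active, 0 sham) and M for the lifestyle programme and coaching (1 given, 0 not given).

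- Group 1: L = 1, M = 1.
- Group 2: L = 0, M = 1.
- Effect of laser given the programme, E(L=1, M=1) − E(L=0, M=1): both terms are observed, so it is estimable.
- Effect of the programme given laser, E(L=1, M=1) − E(L=1, M=0): nobody has M = 0, so it is not estimable at any sample size. The laser-by-programme interaction is not estimable either.

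The literal reading of the Background sentence is therefore unanswerable by this design.

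**Which question each part of the document states.**

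| Place | Component that is added |
|---|---|
| Study title | Laser |
| Overarching purpose (Research Question and Aims) | Laser |
| Hypothesis, opening clause | Lifestyle programme |
| Hypothesis, comparator | Programme alone, so laser is what differs |
| Primary and Secondary Aims | Laser |
| Background, goal sentence | Lifestyle programme |
| Study Design | Laser |
| Data Analysis Plan | Laser (Group 1 against Group 2) |
| Sample-size Justification | Laser |

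Only the Background sentence points wholly the other way. Read to its end, the Hypothesis sets the programme during laser treatment against the programme alone. That is Group 1 against Group 2 except for the sham.

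**The plan's own figure.** Inputs from the Sample-size Justification: difference 1.1 kg, SD 1.6 kg, 30 per group, two-sided alpha 0.05, stated power 75%.

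- Standard error = 1.6 × √(2/30) = 0.413 kg.
- Normal approximation: Φ(1.1/0.413 − 1.96) = Φ(0.70) = 75.9%.
- Noncentral t: 74.5%.

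Both agree with 75%. The sample size was set for laser against sham and fits that question.

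**What pursuing the literal goal would cost.** This is an illustration that assumes the same 1.1 kg and 1.6 kg apply to the new contrasts.

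- A third arm (laser without the programme) within 60 people leaves 20 per arm. The standard error is 1.6 × √(2/20) = 0.506, and power per pairwise comparison is Φ(1.1/0.506 − 1.96) = 58% (56% by the t-test).
- Keeping 30 per arm needs 3 × 30 = 90 people.
- A two-by-two factorial with 15 per cell has an interaction standard error of 1.6 × √(4/15) = 0.826, and power Φ(1.1/0.826 − 1.96) = 26%.

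Nothing in the aims asks for any of these.

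**The case for a change.** The best case for a change is that a protocol should name one question. This one has an overarching purpose under the Aims and an overarching goal in the Background, and they differ. The goal is a statement against which readers may judge the result, and aligning it with the Primary Aim would cost one sentence and an opening clause. The earlier laser studies do not rescue the goal. No historical comparison is planned, it would not be randomized, and the document does not say whether those participants had lifestyle advice. That holds for the fat mass change of −1.1 kg and equally for the weight reductions of 1 to 3.5 kg and circumference reductions of 2.3 to 4.0 cm.

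The mismatch itself stands: the Background sentence does not describe this trial. The harm is not shown. The Data Analysis Plan commits to reporting the difference between treatment groups with a 95% confidence interval, and no section plans a claim that lifestyle change enhances laser. Misreading is possible, but it would require ignoring the title, the aims and the analysis. The Hypothesis gives weaker support than it first seems to, because its comparator already states the contrast the design can test.

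**Conclusion.** This is a clerical inconsistency, and correcting it would change nothing in the trial's conduct or results. One Background sentence names a question that 0 of 60 participants are allocated to answer, and the opening clause of the Hypothesis is clumsy. Every part that governs the trial (aims, arms, endpoint, analysis, sample size) asks whether laser adds to the lifestyle programme, and the two-arm design answers that with the 75% power stated. Arms, sample size and the reported estimate would be identical whichever way the sentence is worded.

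The conclusion assumes that the Primary Aim, rather than the Background narrative, defines the question, and that results are reported as the Data Analysis Plan says. If the investigators did intend to learn what lifestyle change adds to laser, that would be a different trial with a laser-only arm. Nothing in the aims or the analysis suggests they did.

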Medical History & Urine Pregnancy Test		X									
Vitals (weight, height, Body Mass Scale, blood pressure, and pulse)		X	X ¹		X						
Depression (PHQ2)		X					X ²		X ³	X	
Blood specimens (A1C, Lipid Panel, Leptin, Adiponectin, CRP, IL-6, fasting insulin)		X						X		X	
Surveys											
Body Image Questionnaire (BASS)		X					X ²		X ³	X	
Body Appreciation Scale (BAS)		X					X ²		X ³	X	
Perceived Stress Scale (PSS)		X					X ²		X ³	X	
Quality of Life - LASA		X					X ²		X ³	X	
Sleep Impact (ASCQ)		X					X ²		X ³	X	
End of Study Interview (Was It Worth It – WIWI)										X	
Intervention											
Low-Level Laser Therapy/Sham (7) – twice/week			X	X	X	X	X	X			
Lifestyle Modification Introduction and Enrollment		X									
Wellness Coaching Consult, goal setting		X				X			X		
Enrollment into Fitbit® & My Fitness Pal®		X									
Fitbit® and My Fitness Pal® Set up and tutorial for recording steps, activity, and water intake		X									
Fitbit® Data Download (8)			X	X	X	X	X	X		X	
Outcome											
WMA, WC, BMI, WHR (4)		X	X ¹	X ³	X						
InBody Analysis (1) (2) (3) (4)		X	X	X	X	X	X	X	X	X	
Check in on adherence to Lifestyle Modifications			X	X	X	X	X	X	X		

1. Vitals will be collected once a week PRIOR to 2nd treatment of each week (Treatments 2, 4, 6, 8, and 10)

2. These assessments will be collected BEFORE last LLLT intervention of the week.

3. These assessments will be collected AFTER last LLLT intervention.
4. WMA, Weight Motivational Assessments; WC, waist circumference; BMI, body mass index; WHR, waist-to-hip ratio. In order to control for any variance in WC, BMI, or WHR, the visits will be at approximately same time of the day (± 2 hours). These measures will take place at each study visit (once a week during treatment phase).
5. Adverse events (AEs) will be collected at EVERY visit, referencing "since last visit".
6. Concomitant medication information will be collected at EVERY visit, referencing "since last visit".
7. TWICE a week for 6 weeks for a total of 12 treatments.
8. Download weekly data.

Study Measures

Safety Measures:

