- Anthropomorphic Measurements: Measurements will be performed on all participants during all study clinic visits. BMI and WHR will be derived from measurement of weight, height, and waist and hip circumference. The measurements will be as follows: Height and Weight will be measured using the InBody stadiometer scale. Body Mass Index (BMI) will be calculated by InBody. Waist circumference (WC) will be measured while participants are upright. A soft measuring tape will be placed in a horizontal plane at the level of the superior border of the iliac crest. The tape will be snug but not compressing the skin and parallel to the floor. The measurement will be made at the end of a normal expiration.
- Biomarkers: Levels of A1C, CRP, Lipid Panel, Leptin, CRP, IL-6, Adiponectin, fasting insulin will be collected at baseline, week 6 (end of treatment) and week 12 (end of study).
- Was it Worth it Questionnaire (WIWI)²³: This a satisfaction survey will be administered to the participants at the end of the study, probing their satisfaction with the research study. These data could be used to assess the feasibility of the intervention by asking the patient if the entire research experience was worth it for them.

Adherence to Intervention:

- Diary to collect Calorie Intake and Water Intake: My Fitness Pal® will be utilized as an online diary log which the participants can use to record calorie and water intake. This program is linked to the FitBit® (see below). The study staff will educate and assist the participant in setting up a study ID, enrollment and use of both online apps for study purposes. Data from Diary collected on weekly basis.
- Steps: Fitbit® Data from these devices will be collected on weekly basis to download activity levels. A Fitbit® account will be created by each study participant with the help of the research coordinator to allow us to track activity level per week. A weekly report will be sent to their email and this will be logged into the database.
- Treatment Tracking: the study staff will log in the days and times each patient attended an LLLT intervention session during the clinical trial and record the self-report on the lifestyle modifications by the participant.

Intervention:

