The aim of this study is to assess the feasibility and potential efficacy of using LLLT combined with Lifestyle Modification/Wellness Coaching to reduce fat mass and WC in people with obesity or overweight.

The purpose is to decide whether additional studies of the experimental regimen are warranted and to provide preliminary data for designing a larger trial to confirm efficacy. Although there has been debate about the value of formal statistical comparisons in phase II trials, we agree with those who propose that formal comparisons are appropriate under the caveat that phase II studies are not expected to provide reliable definitive comparisons using a traditional two-sided type I error rate of 0.05. Nonetheless, for the present study, a two-sided test with a false-positive (type I error) rate of 0.05 will be used for the primary comparison.

The primary endpoint of the current study is the change in fat mass from baseline. For the primary analysis, the change in WC and fat mass from baseline to week 6 will be compared between groups.

Data Analysis Plan:

Data related to subject recruitment, including the frequency of calls and the reasons for failing screening criteria, will be summarized.

Baseline characteristics and treatment compliance of the enrolled participants will be presented overall and also separately for each of the treatment groups. In all cases, data will be summarized using mean \pm SD for continuous variables and frequency percentages for nominal variables. Treatment adherence will be quantified for each person by calculating the percentage of treatment sessions attended. The percentage of subjects who discontinue study participation and the reasons for discontinuing study participation will be summarized. Changes in measures of central adiposity and weight from baseline will be summarized at each study visit. The primary outcome of interest is the change in fat mass from baseline to week 6. For the primary analysis, the change in fat mass from baseline to week 6 will be compared between treatment groups using analysis of covariance (ANCOVA) with the baseline value included as the covariate. For this analysis, a two-tailed p-value of 0.05 will be considered statistically significant. Similar analyses will be performed for all secondary outcomes. In all cases, findings will be summarized by presenting the point estimate and 95% confidence interval for the difference between treatment groups.

Sample-size Justification:

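### BMI is derived from a height re-measured at the weekly measurement visits, so height-reading error enters BMI change as avoidable noise; using baseline height throughout removes it.

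*Combined protocol and SAP*

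**What the plan says.** In the Combined protocol and SAP, Outcome Measures, Anthropomorphic Measurements, the plan says:

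- on timing: "Measurements will be performed on all participants during all study clinic visits";
- on derivation: "BMI and WHR will be derived from measurement of weight, height, and waist and hip circumference";
- on source: "Height and Weight will be measured using the InBody stadiometer scale", followed by "Body Mass Index (BMI) will be calculated by InBody".

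The schedule under Study Process has a safety row that begins "Vitals (weight, height, Body Mass Scale, blood pressure, and pulse", so height is one of the vitals. Its first footnote says "Vitals will be collected once a week PRIOR to 2nd treatment of each week". BMI itself sits in the Outcome block of the schedule, and footnote 4 has it taken at each study visit, once a week during treatment. The same footnote tries to limit variation in waist circumference, BMI and waist-to-hip ratio by holding visits to about the same time of day, within 2 hours.

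The Data Analysis Plan specifies ANCOVA on change in fat mass with the baseline value as covariate, and adds: "Similar analyses will be performed for all secondary outcomes". Nothing in the document says that baseline height is carried forward.

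**The concern.** Within one adult over 6 to 12 weeks, true BMI change is weight change divided by a constant. A second height reading adds no information about that change. It adds the error of two readings, and because height is squared, each relative error counts twice. A participant whose weight has not moved can then be recorded as gaining or losing BMI, and the BMI and weight results can disagree for no biological reason. The same-time-of-day rule reduces diurnal variation in height but not posture or reading error.

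What is at stake is the width of the confidence interval for the group difference in BMI change.

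**Working it through.** **The plan's own figure.** Sample-size Justification gives 30 per group, a difference of 1.1 kg, SD 1.6 kg and two-sided alpha 0.05, all for fat mass. The standard error is 1.6 × √(2/30) = 0.413 kg and 1.1/0.413 = 2.66. Power is Φ(2.66 − 1.96) = 75.9% by the normal approximation and 74.5% by the noncentral t with 58 degrees of freedom. The stated 75% reproduces. It contains no BMI term, so it does not change below.

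**A single record.** Weight is 90 kg at both visits; height is read as 168.0 cm, then 167.5 cm.

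- Baseline BMI: 90/1.680² = 31.89.
- Later BMI: 90/1.675² = 32.08.
- False change: +0.19 kg/m², equivalent to 0.19 × 1.68² ≈ 0.54 kg of weight that was not gained.

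**Across participants.** Inputs that are not in the documents and are therefore assumptions:

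- SD of one height reading, s_h: 0.3 to 0.5 cm.
- SD of weight change: 1.6 kg (the plan's fat-mass SD, borrowed) or 2.5 kg.
- Typical participant: 1.68 m, BMI 31.9, within the eligible range of 25 to 39.9.

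Formulas:

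- Error SD of BMI change = √2 × 2 × BMI × s_h / height.
- SD of BMI change with height fixed = SD of weight change / height².
- Variance inflation = 1 + (error SD / fixed-height SD)².

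Results:

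- Error SD at s_h = 0.3 cm: √2 × 2 × 31.9 × 0.003/1.68 = 0.16 kg/m². At 0.5 cm: 0.27 kg/m².
- Fixed-height SD: 1.6/2.822 = 0.57 kg/m², or 2.5/2.822 = 0.89 kg/m².

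| Height-reading SD | Weight-change SD 1.6 kg | Weight-change SD 2.5 kg |
|---|---|---|
| 0.3 cm | variance +8% | variance +3% |
| 0.5 cm | variance +22% | variance +9% |

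The confidence interval widens with the square root of the variance: about 4% and 11% in the first column, 2% and 4% in the second.

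The inflation depends on BMI. At 1.70 m with a weight-change SD of 1.6 kg, it is 5% and 14% at BMI 25, and 13% and 36% at BMI 39.9, for reading SDs of 0.3 and 0.5 cm.

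**Check by simulation.** ANCOVA with 30 per arm (mean height 1.70 m, mean BMI 32, weight-change SD 1.6 kg, 1,500 runs) gave a mean standard error for the BMI difference of 0.146 with no height error, 0.151 at 0.3 cm and 0.161 at 0.5 cm. The mean estimate stayed between −0.381 and −0.388, so the loss is of precision and the comparison is not biased.

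**What remains after the fix.** An error in the single baseline height only rescales that person's BMI change. A 0.5 cm error at 168 cm alters it by about 2 × 0.5/168 = 0.6%.

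**The case against.** The strongest reply is that little depends on BMI. The primary endpoint is fat-mass change and the one named secondary aim is waist circumference. Study Design lists weight, waist circumference, A1C and CRP as the changes to be assessed, without BMI. The Data Analysis Plan's reference to all secondary outcomes does not name it either. With height fixed, BMI change is weight change rescaled by each person's height, and weight change is already summarised free of height error. All of this stands, and it limits the point to a small improvement.

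Second, the documents do not say whether the device takes a new height or reuses a stored one when it calculates BMI. That also stands. But the text says height is measured, places it among the weekly vitals and derives BMI from it, so re-measurement is the literal reading. It applies to the weekly measurement visits, not to both treatment sessions in a week or to the phone contact. The columns of the vitals row did not survive extraction well enough to say exactly which later visits are marked.

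Third, Study Procedures promises standardized methods and data-entry checks for implausible or inconsistent values. These may catch a gross height discrepancy; they would not remove an error of half a centimetre.

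Fourth, the size rests on assumed inputs. That is right. The 1.6 kg is a fat-mass SD, and a larger weight-change SD shrinks the inflation. A power figure for BMI would also have to borrow the 1.1 kg fat-mass difference as a BMI effect, so none is offered here.

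A reader might infer that the same height error contaminates fat mass, since the InBody produces both. The documents do not describe how the device uses height in its body-composition calculation, so they do not support that inference.

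**Conclusion.** The point holds as a minor, free improvement. As written, the plan lets height-reading error into BMI change at the weekly measurement visits, and nothing fixes height at baseline. The cost is precision for BMI, an outcome outside the stated aims. Under the assumed reading SD of 0.3 to 0.5 cm, the variance of BMI change rises about 8 to 22% with a weight-change SD of 1.6 kg, and about 3 to 9% with 2.5 kg. These ranges illustrate the size and do not estimate what occurred in this trial.

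Two stronger readings are not supported. The treatment comparison is not biased, because reading error does not depend on arm. The trial's 75% power is not reduced, because it concerns fat mass.

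**What to change.** In Anthropomorphic Measurements, state that BMI at every visit is the weight at that visit divided by the square of baseline height. In the schedule, remove height from the post-baseline vitals cells as a measurement used for BMI. For participants already measured, recompute BMI from stored weight and baseline height.

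This costs one sentence, one schedule edit and a short derivation in the analysis code, with no added visits or staff time. It can be applied after data collection is complete. How height is entered in the InBody should be left as it is, because the documents do not describe how the device uses it and the same device supplies the primary endpoint.
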